6.1 Sample Size Determination

Based on a study of BIRADS grading of a mammography registry, 80% of all screening mammograms are BIRADS 1 and 2. The incidence of malignancy should be 1-2% of all screening mammograms. The screening center performs 11,000 screening mammograms a year plus over 3000 biopsies. About 600 breast cancers are diagnosed yearly. Since symptomatic individuals scheduled to undergo diagnostic imaging or biopsy are eligible to participate this will enrich the population categorized to BIRADS 3-5. Using a sample size of 1000 subjects provides 80% power.

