4.3 Subject Recruitment and Screening

Subjects will be offered participation in the study during their visit to the Women’s Imaging Center by the PIs, [name], [name], and/or their designee. This study may recruit up to 1000 subjects. Patient’s will be eligible for study participation if they have a scheduled visit for the Women’s Imaging Center and have not previously participated in this study. The reason for the patient’s visit, screening or diagnostic, will not affect their eligibility. Diagnostic visits are included as it is necessary to ensure the accuracy of the iBE device’s ability to detect BIRADs 3-5. The iBE device was created to use as a screening tool to detect clinically relevant breast lesions, defined here as BIRADs 3-5, with the purpose of giving patients proper follow-up recommendations without causing unnecessary anxiety of avoidable diagnostic tests.

5 Study Procedures

Participants will be recruited from the Women’s Imaging Center who are scheduled to undergo screening or diagnostic imaging including biopsies. Subjects will have the study explained to them and given the consent form to review early in their imaging center visit. After the subjects have had time to review the consent, the PI or designee will answer all questions. If she/he agrees and signs the consent form, they will receive a signed copy to take home with them. All subjects must meet the inclusion and exclusion criteria. Consent will be obtained prior to any study-related activities.

The iBE evaluation will be performed by a trained individual who is blinded to the outcome of the radiology studies at the time the iBE is performed. The trained individual will be a healthcare worker with minimum education (or equivalence) to a licensed practical nurse (LPN) or an ultrasound tech. This is the target education level for the intended iBE operators. The selected healthcare worker will be trained by [name], MD to administer the iBE and clinical breast exams. The trainee will follow [name] during clinic hours for 1-2 days and trained for clinical breast exams, similar training to a medical student. The iBE training will mostly be software and instrument training by the leading iBE user in the United States, [name]. A minimum of two healthcare workers will be trained.

[figure not shown]

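### The 80% power in section 6.1 carries no alpha, endpoint or number of reference-positive subjects, and the log z-test planned in 6.2 exceeds its nominal error

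*Combined protocol and SAP*

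**What the plan says.** Section 6.1 gives background figures and then one sentence on power: "Using a sample size of 1000 subjects provides 80% power". The figures are that "80% of all screening mammograms are BIRADS 1 and 2" and that "The screening center performs 11,000 screening mammograms a year plus over 3000 biopsies". On symptomatic subjects it says only that "this will enrich the population categorized to BIRADS 3-5".

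Section 4.3 treats the total as a ceiling: "This study may recruit up to 1000 subjects". The reason for the visit, "screening or diagnostic, will not affect their eligibility". It also explains why diagnostic visits are there: "Diagnostic visits are included as it is necessary to ensure the accuracy of the iBE" device's detection of BIRADS 3-5.

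Section 6.2 computes sensitivity as TP/(TP+FN), expects 0.95 for sensitivity and 0.92 for specificity, and tests each against a boundary five per cent lower, using a z-score on the log scale with delta-method variance.

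**The concern.** The denominator of sensitivity is the reference-positive subjects, so a total of 1000 does not fix its power. The plan recognises that case mix matters, since it admits diagnostic visits for that reason. But it gives neither an expected number of positives nor the alpha, and it does not say whether the 80% refers to sensitivity, specificity, both, or the comparison with clinical breast examination. A reader cannot tell under what conditions the figure holds.

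The second issue is the test. Close to a proportion of 1, a z-test whose variance is estimated from the observed proportion can reject too often. Any power figure based on it would then look better than it is.

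Section 2 says the results are needed to prepare an international trial. If sensitivity missed its boundary with few positives, the plan would give no yardstick for whether the study could have succeeded. If it met the boundary, the stated error rate would be too low.

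**Working it through.** **Inputs from the documents.** Sensitivity 0.95 and specificity 0.92 (6.2). Boundaries five per cent lower (6.2): absolute 0.90 and 0.87, or relative 0.95 × 0.95 = 0.9025 and 0.92 × 0.95 = 0.874; the text does not say which. Screening share outside BIRADS 1-2: at most 20% (6.1). Centre volumes: 11,000 screening mammograms and 3000 biopsies (6.1). Half of the 44 patients in the diagnostic pilot were BIRADS 3 or 4 (1.6).

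**Assumptions, not plan figures.** One-sided alpha 0.025 or 0.05; enrolment in proportion to the centre volumes, counted as separate visits; 5% screening positivity as a low case. Paired results below are for boundary 0.90 / 0.9025.

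**1. Can the 80% be reproduced?** Not from stated inputs. It appears with 20% positives, one-sided 0.05, boundary 0.9025 and the untransformed formula with null variance in the alpha term:

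n = [(1.645 √(0.9025 × 0.0975) + 0.842 √(0.95 × 0.05)) / 0.0475]² ≈ 200 positives, and 200 / 0.20 = 1000.

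The log-scale formula with delta-method variance at 0.95, closer to 6.2, gives (1.645 + 0.842)² × (0.05/0.95) / (ln(0.95/0.9025))² ≈ 124 positives, or 620 subjects at 20%. The match at 1000 therefore needs choices that the plan does not state.

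**2. How many positives?**
- Screening visits only, upper limit: 1000 × 0.20 = 200.
- Assumed mix: 3000/14,000 = 21%, so 214 biopsy and 786 screening visits. With 50% and 20% positive: 107 + 157 = 264.
- Same mix with 5% at screening: 107 + 39 = 146.
- Same mix with all biopsy visits positive and 20% at screening: 214 + 157 = 371.

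**3. Exact binomial test, one-sided 0.025, true sensitivity 0.95.** Reject at the smallest count c with P(X ≥ c | n, boundary) ≤ 0.025; power is P(X ≥ c | n, 0.95).

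| Positives | Reject from | Power |
|---|---|---|
| 146 | 139 / 139 | 55% / 55% |
| 200 | 189 / 189 | 70% / 70% |
| 264 | 248 / 248 | 83% / 83% |
| 371 | 346 / 347 | 95% / 92% |

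At one-sided 0.05 with 200 positives the test rejects from 188 for either boundary, with power 79.6%.

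**4. The log z-test of 6.2.** z = (ln p̂ − ln p0) / √((1 − p̂)/(n p̂)). With n = 200 and p0 = 0.90, 187 successes give ln(0.935/0.90) / √(0.065/187) = 0.0382/0.0186 = 2.05, above 1.96; 186 give 1.69, below it. Rejection therefore starts at 187, and P(X ≥ 187 | 200, 0.90) = 5.7%.

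| n = 200 | Reject from | Actual error |
|---|---|---|
| nominal 2.5% | 187 / 188 | 5.7% / 4.1% |
| nominal 5% | 186 / 187 | 9.3% / 7.1% |

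At nominal 2.5% its power is 87% / 80%. With boundary 0.9025 it rejects from 188, exactly where the exact test at 0.05 does. Its 80% there is the power of a test with 4.1% error. At 146 positives the actual error is 7.3% / 4.7%; at 371 it is 4.4% / 4.1%.

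**5. Specificity.** At true specificity 0.92 with 629 to 900 reference-negative subjects, power is at least 96% under every variant tried (both alphas, both boundaries, z and exact tests). Sensitivity is the limiting measure.

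**6. Positives for 80% exact power at 0.95.** Exact power moves in steps. It stays at or above 80% from 255 / 274 positives at 0.025, and from 203 / 221 at 0.05. At 0.025 it first touches 80% at 231 / 249.

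**The case against.** Section 6.1 does offer a basis. At most 20% of screening mammograms fall outside BIRADS 1-2, which suggests about 200 positives per 1000, and enrichment should add to that. At 200 the 80% is roughly recovered, and at 264, using the plan's own screening figure, even the exact test at 0.025 exceeds 80%. The 55% needs a 5% screening positivity that appears nowhere in the documents. **All of this stands.** What remains is that the 20% is an upper limit for a population that 6.1 itself says will differ from the study's, and that at 200 positives the answer is 80% or 70% depending on an unstated alpha.

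A reader might infer that the study is underpowered. The documents do not support that, because they fix neither the mix nor the alpha. A reader might also set the 40/46 (87%) in 1.6 in place of 0.95. That figure is per lesion and from an earlier 1x4 probe, so it is a reason to ask where 0.95 comes from, and no alternative planning value.

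A binding minimum number of positives would also go too far. It depends on the choice of alpha and on requiring power to stay above 80%. It might mean steering recruitment by visit type, against 3.1 and 4.3, which open the study to all visits.

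The exact test may be called conservative: its actual error with 200 positives is 1.7% / 2.2% at 0.025. But the next lower rejection count, 188, has 3.2% / 4.1%, so no cut-off on the count comes closer without exceeding 2.5%.

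**Conclusion.** The point holds as a gap in the power statement and a flaw in the planned test; it does not show that the power is inadequate. The 80% in 6.1 lacks the alpha, endpoint and number of positives that would give it meaning. At true sensitivity 0.95, exact power at one-sided 0.025 is 55%, 70% and 83% with 146, 200 and 264 positives. The 264 rests on the assumed visit mix and the pilot's 50%, the 146 additionally on an assumed 5%, and 200 is the screening-only upper limit.

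The excess error of the log z-test does not depend on which usual alpha was meant: with 200 positives it is 5.7% / 4.1% at nominal 2.5% and 9.3% / 7.1% at nominal 5%. Part of that test's apparent power is therefore bought with false-positive error. This should be fixed before analysis. It is no ground for enlarging the study.

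**What to change.** 1. In 6.2, state alpha, its sidedness and the boundaries as numbers (0.90 or 0.9025 for sensitivity; 0.87 or 0.874 for specificity). Replace the log z-test with an exact binomial test, or another test that holds its error.
2. In 6.1, restate power on that test, for sensitivity conditional on the number of reference-positive subjects and for specificity separately. Give the expected number of positives with its assumed visit mix, and the data set and counts behind 0.95 and 0.92.
3. Optionally, within the 1000 cap, track positives from the scheduled imaging or biopsy against the number for 80% exact power (about 255 / 274 at one-sided 0.025, about 203 / 221 at 0.05). Leave out of this count positives found only through ultrasound prompted by iBE, because the device can create them. If the number is not reached, report the achieved count and the confidence interval.
4. Optionally, report sensitivity by visit type as a descriptive result, since 4.3 says: "The iBE device was created to use as a screening tool to detect clinically relevant breast lesions".

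Items 1 and 2 cost only wording, but give a less favourable power statement and lower nominal power than the log z-test. Item 3 needs a running count with late biopsy results. That count may differ from the denominator analysed, and is not fully independent of the device because the radiologist sees the iBE report. Intervals in item 4 may be wide: 37/39 gives 0.827 to 0.994.

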6.2 Statistical Methods

Data will be analyzed using contingency table methods, estimating the sensitivity and specificity of the device to correctly assign subjects to BIRADS 1, 2 versus BIRADS 3, 4, 5 categories. Sensitivity is calculated from contingency table counts as $TP/(TP+FN)$, and specificity is calculated as $TN/(TN+FP)$, (and will be log transformed) with variances obtained using the delta method. Both sensitivity and specificity measures are expected to be high, given great performance in preliminary data (0.95 and 0.92 respectively). We will use a non-inferiority approach, attempting to demonstrate that in the clinical setting, iBE matches our preliminary values, and we will test them against null hypothesis values (Non inferiority boundaries) that are 5% below our preliminary data using the z-score for the log-transformed measure.

	Mammogram BIRADS 1,2	Mammogram BIRADS 3,4,5 or biopsy positive (same breast and same quadrant)
iBE negative	True Negative (TN)	False Negative (FN)
iBE positive	False Positive (FP)	True Positive (TP)

And to CBE as a primary comparison

	CBE negative	CBE positive
iBE negative	True Negative	False Negative
iBE positive	False Positive	True Positive

7 Safety and Adverse Events

Due to the nature of this device and our experience thus far, adverse effects are not anticipated, however, the investigator will follow the processes below should an event occur.

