1.6 Clinical Data to Date

In Vivo Testing: Forty *in vivo* evaluations of the 1x4 PEF-compression probe were conducted by [name] at his Hahnemann Hospital outpatient office under an IRB-approved protocol. These evaluations were performed for device development, not clinical utility. The probe was tested with various pushing depth, i.e., at 2 mm, 4 mm, or 6 mm pushing depths to assess the effect of different pushing depth on the measured elastic modulus map. The results showed that different pushing depths did not alter the tissue elastic map, in terms of the lesion location and size. The PEF measurements were compared to patients' mammography reports. All tests were blinded.

A total of 40 patients were enrolled and 46 lesions were confirmed by imaging or pathology. PEF reported 55 lesions, with 9 false positives and 2 true positives not originally found on imaging or palpation. The overall sensitivity of the PEF test was 40/46 or 87%. In women 40 years or younger the overall sensitivity was 19/19 or 100%. In women who had a lesion visible on mammography, PEF had a sensitivity of 83% (24/29). Of these, in women aged 40 or younger, PEF identified all 7 mammographically visible lesions, including 2 malignant lesions. When compared with ultrasound, PEF correctly identified 87% (34/39) in this group. Of these, in women aged 40 or younger, PEF identified 100% (19/19) of all ultrasound visible lesions.

UPenn Clinical Pilot Study

A total of 44 patients were enrolled in this prospective signal processing/algorithm development trial. Patients presenting to the Pennsylvania Hospital Women's Imaging Center for breast diagnostic services including ultrasound and/or diagnostic mammogram and/or needle biopsy were recruited for an iBE exam prior to biopsy. The final production prototype device was used for all studies.

The demographic result of the patient population is 59% Caucasian 34% African Americans, 2% Asian, and 4.5% unknown with an average age of 41 with one male having participated in the study. The patient population is comprised of those who needed breast diagnostic services of the 44 patients 50% were determined to be BIRADs 2, and the other 50% were BIRADs 3 or 4, zero patients were categorized BIRADs 1 or 5. 17 subjects of underwent a biopsy.

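### Section 6.2 does not say where the delta-method variance is evaluated; at the observed proportion, the sensitivity test averages 1.5 to 1.8 times an assumed one-sided alpha of 0.05 or 0.025.

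*Combined protocol and SAP*

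**What the plan says.** Section 6.2 estimates sensitivity as TP/(TP+FN) and specificity as TN/(TN+FP) ("and will be log transformed) with variances obtained using the delta method"). The values expected are 0.95 and 0.92. The null values are described as "Non inferiority boundaries) that are 5% below our preliminary data", and each is tested "using the z-score for the log-transformed measure". The section does not say whether the variance uses the observed proportion or the null value, or whether 5% is absolute or relative. No alpha or sidedness appears anywhere in the document.

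Section 6.1 states "Using a sample size of 1000 subjects provides 80% power". It names no test, endpoint or number of reference-positive subjects. It puts 80% of screening mammograms at BIRADS 1 and 2 and says of including symptomatic patients that "this will enrich the population categorized to BIRADS 3-5", without a figure.

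**The concern.** The delta method gives Var(log p) = (1-p)/(np). With the observed proportion put in, this variance shrinks as the estimate rises. Near 0.9, the samples that by chance run high also get the smallest standard error, so the z-score is too large exactly where it decides the test. A non-inferiority test with this feature passes a device sitting on the boundary more often than its nominal level allows.

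Two things are at stake. This z-score is the plan's only stated non-inferiority test, and Section 2 says the results are needed to prepare an international trial. And while the variance is left open, a borderline result could pass or fail by a choice made after the data are seen.

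**Working it through.** **Inputs from the plan.** Expected sensitivity 0.95 (6.2). Boundary p0 = 0.95 - 0.05 = 0.90 if the 5% is absolute, or 0.95 x 0.95 = 0.9025 if relative. Up to 1000 subjects (4.3). About 20% BIRADS 3-5 in a screening mix (6.1), so about 200 positives before enrichment.

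**Assumptions.** One-sided alpha 0.025 or 0.05; 200 to 400 positives (the upper end is not in the plan); one result per subject. Pairs below are for alpha 0.025 / 0.05.

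**The plan's 80% power.** It cannot be reproduced uniquely, because alpha and the number of positives are missing. Exact power with 200 positives and true sensitivity 0.95:

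| Boundary | Variance at observed p | Variance at p0 |
|---|---|---|
| 0.90 | 87.0% / 92.2% | 70.0% / 79.6% |
| 0.9025 | 79.6% / 87.0% | 70.0% / 79.6% |

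So 80% is matched, at 79.6%, under either variance, depending on the alpha and margin chosen.

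**One worked count.** n = 200, p0 = 0.90, alpha 0.025 (critical value 1.96), 187 detected, p = 0.935:

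- Log difference: ln(0.935/0.90) = 0.03815.
- Variance at observed p: SE = sqrt(0.065/(200 x 0.935)) = 0.01864; z = 2.05, pass.
- Variance at p0: SE = sqrt(0.10/(200 x 0.90)) = 0.02357; z = 1.62, fail.

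With the observed variance the test passes from 187 detected, and P(X >= 187 | n = 200, p = 0.90) = 5.7%. With the boundary variance it passes from 189, with exact size 1.7%. The score and exact tests also need 189. At boundary 0.9025 the cut-offs are 188 for the observed variance and 189 for the other three.

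**Average type I error.** For each n the rejection region was found and its exact binomial probability at p0 = 0.90 summed; every n from 200 to 400 has equal weight.

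| Test | alpha 0.025 | alpha 0.05 |
|---|---|---|
| Log z, variance at observed p | 4.4% | 7.3% |
| Untransformed Wald | 4.2% | 7.0% |
| Log z, variance at p0 | 1.8% | 4.2% |
| Score | 2.0% | 4.5% |
| Exact binomial | 1.9% | 4.0% |

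At p0 = 0.9025 the first row is 4.5% / 7.4%. The ratios are 4.42/2.5 = 1.77 and 7.30/5 = 1.46 at 0.90, and 1.78 and 1.48 at 0.9025. Single counts from 200 to 400 run from 1.35 to 2.5 times alpha at 0.025 and from 1.2 to 1.95 times at 0.05. The error is above the assumed alpha at every count from 100 to 500, under both boundaries. The Wald row shows that the cause is the plug-in variance and not the log.

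**What this means for the boundary (p0 = 0.90).** The observed-variance test passes at exactly its assumed level when true sensitivity is 0.8952 / 0.8965 on average. That lowers the boundary by 0.90 - 0.8952 = 0.48 or 0.90 - 0.8965 = 0.35 percentage points, with a range of 0.1 to 0.9 at single counts. A true 0.89 passes 1.3% / 2.4% of the time. A true 0.87, the figure Section 1.6 reports for the earlier probe (40/46), passes 0.1% / 0.2%.

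**Positives needed for power of at least 80% at that count and every larger one examined (up to 600), true 0.95:**

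| Boundary | Log z, observed p | Score | Exact |
|---|---|---|---|
| 0.90 | 185 / 150 | 254 / 188 | 255 / 203 |
| 0.9025 | 203 / 166 | 273 / 205 | 274 / 221 |

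**Specificity.** At boundary 0.87 with an assumed 600 to 800 negatives the average is 3.5% / 6.2%, or 1.4 / 1.2 times alpha.

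**The case against.** The strongest reply is that the excess is measured against an alpha the plan never states and on one of two possible readings. A test against stated null values can properly use the null variance, and then there is no average excess. The 80% power figure does not settle it, since either variance can match it. At a one-sided 0.10 the ratio falls to about 1.25. This stands as a limit on the multiple. It does not remove the gap: putting the estimate into the variance is the ordinary meaning of a delta-method variance for a proportion from table counts, and if the team intends the null variance, the plan needs to say so.

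The effect is also small in practice. It is under half a percentage point on average, and a device at 0.87 almost never passes. The study has no stated success rule and does not affect clinical decisions. This stands and bears on how serious the point is.

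The score test can itself exceed alpha. At 200 positives, boundary 0.90 and alpha 0.05 its size is 5.7%. That is true, but the observed-variance test has 9.3% at the same count, and the exact test is available if no excess is acceptable.

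Finally, the reference table in 6.2 asks for agreement on breast and quadrant. If results were counted by lesion or quadrant, the counts would change, clustering would enter, and these rates would not carry over.

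**Conclusion.** The concern holds and should be fixed. Section 6.2 leaves the variance open, and on its ordinary reading the sensitivity test is anti-conservative: on average 1.8 times an assumed one-sided 0.025, or 1.5 times 0.05, over 200 to 400 positives. The direction does not depend on that range or on how the 5% is read. The size depends on the assumed alpha, on the range of positives and on one result per subject. It is a real but narrow error in a single test. The plan states no overall success rule, so nothing is claimed about an overall decision. The open choice matters at least as much for Section 6.1, where the roughly 200 positives implied by the screening mix lie between the 185 and 254 that two reasonable tests need at alpha 0.025 and boundary 0.90.

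**What to change.** In Section 6.2, name a one-sided score test, z = (p - p0)/sqrt(p0(1-p0)/n) with p0 the boundary, and report the matching Wilson interval. On average it is at or below nominal. Its worst case over 100 to 500 positives is 2.6% / 5.9% at boundary 0.90 and 2.7% / 6.0% at 0.9025. If alpha must never be exceeded, use an exact binomial test with a Clopper-Pearson interval and accept that it is conservative. The smallest edit is to keep the log z-score and fix its variance at p0. Dropping the log alone does not help. State alpha, sidedness and whether the 5% is absolute or relative.

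In Section 6.1, restate the 80% power for the chosen test, with the expected number of reference-positive subjects.

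This is a text change made before results are seen, with no new data. The cost is power. With 200 positives, true 0.95 and boundary 0.90, power at 0.025 is 70% (score or exact) against 87% with the observed variance; at 0.05 it is 87% (score) or 80% (exact) against 92%. The 254 positives that the score test needs at 0.025 are about 25% of 1000. The intended enrichment may reach that, but 6.1 gives no target to check it against.

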1.3 Health worker led “earlier detection”

The American Joint Committee on Cancer (AJCC) staging system indicates prognosis based on the size of the tumor at detection viz. stage of breast cancer. Identifying tumors at earlier stages (down-staging) can improve survival, assuming high-quality treatment is accessible. In the U.S., approximately 40 million women receive mammograms annually and roughly 232,000 new cases are identified; vast majority are detected at stage Tis and T1 with a 5-year survival of 100%. In the context of LMICs, where up to two-thirds of breast cancer cases present at late stages, systematic down-staging is required, such that majority of the cases would be identified at Stage II or earlier, where survival can be 93% or better (again, assuming treatment is available).

In LMICs, health workers, nurses and midwives represent the most affordable resource to bridge the accessibility gap due to the lack of secondary prevention programs like in HICs. What is needed is a low-cost, user-friendly technology that can be used by health workers with minimal training to administer standardized breast exams without any special infrastructure with the goal to down-stage breast cancer to at least Stage II. The low-cost technology must perform with better detection sensitivity than CBE (higher than 50%) and equally high specificity as CBE (94%) to accurately and effectively identify breast lumps in need of further diagnostic follow-up (diagnostic ultrasound, breast biopsy) without clogging the under-resourced infrastructure with false positives due to typical benign breast features (tissue variability, lumpiness and nodularity).

Contrast in elastic stiffness between normal and abnormal breast tissue has long been recognized (Harris '94). Breast cancers are known to be stiffer than normal breast tissues. Major medical device manufacturers are exploring different sensing mechanisms like Ultrasound Elastography and MRI, which use tissue stiffness to differentiate between malignant and non-malignant tissue.

[figure not shown]

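### Passing the section 6.2 specificity test shows consistency with the preliminary value, not specificity as high as CBE, and no planned analysis addresses the latter

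*Combined protocol and SAP*

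**What the plan says.** Section 1.3 sets out what a device for low- and middle-income countries has to achieve: "The low-cost technology must perform with better detection sensitivity than CBE (higher than 50%) and equally high specificity as CBE (94"%). The reason given is to find lumps that need follow-up "without clogging the under-resourced infrastructure with false positives".

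Section 6.2 expects high values, "given great performance in preliminary data (0.95 and 0.92 respectively"), for sensitivity and specificity in that order. The approach is non-inferiority, "attempting to demonstrate that in the clinical setting, iBE matches our preliminary values". Each measure is tested against "null hypothesis values (Non inferiority boundaries) that are 5% below our preliminary data", "using the z-score for the log-transformed measure". The boundary values are not printed, and the section does not say whether 5% is absolute or relative.

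Section 6.2 then adds a second table, called a primary comparison, which cross-classifies iBE against CBE. In it, CBE-negative and CBE-positive take the place of the reference result: iBE positive with CBE negative is a false positive, and iBE negative with CBE positive is a false negative.

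Section 2 says the results are needed to prepare an international trial in low- and middle-income countries. Section 5 gives every subject a bilateral iBE and a bilateral CBE.

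**The concern.** The need in section 1.3 is relative: specificity as high as CBE. The only formal test of specificity asks whether iBE holds up against its own preliminary value less 5%. The expected value and both readings of the boundary lie below the CBE figure quoted in section 1.3, and no section links the two or explains why a lower value would do.

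What is at stake is the claim drawn from a pass. The results feed a trial in the setting where false positives are said to matter most. A pass could be carried forward as support for CBE-level specificity when it was not designed to show that. The one analysis that names CBE cannot supply the answer either.

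Sensitivity is not affected. Its boundary, 0.90 or 0.9025, is far above the 50% in section 1.3.

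**Working it through.** **Inputs.**
- CBE specificity 0.94 (section 1.3).
- Expected iBE specificity 0.92, boundary 5% lower (section 6.2).
- 1000 subjects, with 80% of screening mammograms BIRADS 1-2 (section 6.1). This gives at most about 1000 × 0.80 = 800 reference-negatives. Section 6.1 also expects enrichment for BIRADS 3-5, of unstated size, which lowers the number. In the pilot in section 1.6, half the patients were BIRADS 3 or 4; that mix would give 500.
- Alpha and sidedness are not stated. One-sided 0.025 is assumed.

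**The plan's own figure.** Section 6.1 says "Using a sample size of 1000 subjects provides 80% power". This cannot be reproduced, because endpoint, alpha, sidedness and case mix are missing. The nearest variant is for sensitivity (200 positives, boundary 0.9025, one-sided 0.05, null variance), which gives 79.0%. For specificity with 800 negatives, power exceeds 99% in every variant tried. Nothing below depends on the 80%.

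**Boundary.** 0.92 − 0.05 = 0.87, or 0.92 × 0.95 = 0.874. Both are below 0.94, as is 0.92.

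**Pass point.** z = ln(p/p0) / √[(1 − p)/(np)], pass if z > 1.96. With n = 800 and p0 = 0.87:
- 713/800: 0.02413 / 0.01235 = 1.95, fails.
- 714/800 (89.3%): 0.02553 / 0.01227 = 2.08, passes. Exact 95% interval 86.9% to 91.3%.
- 737/800 (92.1%) is the highest count whose exact upper limit (93.9%) is still below 94%.

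So every count from 714 to 737 passes with an interval wholly below 0.94. The chance of such a result is the binomial probability of that range.

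**Chance of passing with the exact 95% interval wholly below 0.94, true specificity 0.92.**

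| Reference-negatives | Boundary 0.87: counts | Chance | Boundary 0.874: counts | Chance |
|---|---|---|---|---|
| 800 | 714–737 | 57% | 716–737 | 57% |
| 600 | 537–551 | 45% | 539–551 | 44% |
| 500 | 449–458 | 36% | 450–458 | 35% |
| 400 | 360–365 | 25% | 362–365 | 20% |
| 300 | 271–273 | 17% | 272–273 | 12% |
| 200 | none | 0 | none | 0 |

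A log-scale interval gives slightly lower chances, for example 52% in place of 57% at 800 with boundary 0.87.

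**False positives per 800 reference-negatives.** 800 × 0.13 = 104 at 0.87, 800 × 0.08 = 64 at 0.92, and 800 × 0.06 = 48 at 0.94.

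**The CBE table.** Specificity from this table is the share of CBE-negative subjects who are iBE-negative. Two devices in perfect agreement would score 100% whatever their true specificity. A lesion that iBE finds and CBE misses counts as a false positive; a CBE false alarm that iBE correctly leaves negative counts as a false negative. The table measures agreement, and neither test's specificity can be recovered from it.

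**The case against.** A reader might infer that the trial can declare success with data that rule out its own requirement. The documents do not support this, for three reasons, and all three stand.

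- The 94% appears once, in the background, as a need for the technology. The objective (section 2) is to measure accuracy, the endpoint (section 3.2) is to determine sensitivity and specificity, and section 6.2 limits the test to matching the preliminary values. No section defines trial success or says that a pass meets the need in section 1.3. Testing replication is legitimate.
- The comparison with 0.94 may not be like for like. Section 1.3 gives no reference standard or population for it, while this trial scores specificity against BIRADS 1-2 in an enriched sample. The need is also relative: if CBE specificity here were, say, 0.91, an iBE specificity of 0.92 would satisfy it with an interval below 0.94.
- The size depends on case mix. The 57% belongs to the upper bound, and at 200 negatives the overlap disappears.

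It can also be said that section 6.2 already estimates specificity with its variance, so a reader can see where it falls against 94%. That is so, and a further interval set against a fixed 0.94 would add little. It does not fill the gap, because the relevant comparator is CBE in the same subjects, and the planned CBE table does not provide it.

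**Conclusion.** The point holds in limited form. Rejecting 0.87 or 0.874 shows that iBE specificity is consistent with the preliminary value within the margin. It does not show specificity as high as CBE, and no planned analysis does. This holds at any sample size and under either reading of the 5%.

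The figures illustrate the gap and are not a failure rate against a trial criterion. At true specificity 0.92, a pass with an interval wholly below 0.94 occurs in 57% of trials at 800 reference-negatives, falling to zero at 200. They rest on one-sided 0.025, the log z test with the variance at the observed proportion, exact intervals, and 0.94 taken as a fixed benchmark. Nothing here suggests that the specificity estimate is biased, or that the replication test should be dropped.

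**What to change.** Keep the replication test. In section 6.2, replace the CBE-as-reference table with a paired comparison in which iBE and CBE are each scored against the imaging/biopsy reference, with the same rule for matching breast and quadrant.

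Among the n reference-negative subjects, let b be the number iBE-negative and CBE-positive, and c the number iBE-positive and CBE-negative. Report the iBE minus CBE specificity difference, (b − c)/n, with a 95% confidence interval from a paired (McNemar-type) method. A simple standard error is √[b + c − (b − c)²/n] / n. Base any statement of CBE-level specificity on this difference. If a formal non-inferiority claim against CBE is wanted, its margin must be set in advance, since the documents give none.

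One caution for the write-up: section 5 adds an ultrasound for iBE findings that the mammogram leaves unresolved and states no equivalent for CBE findings. The plan should therefore say how reference status is fixed for both tests.

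Cost: one analysis on data already to be collected from every subject, some wording in section 6.2, and a conclusion that may be less favourable to the device.
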